Creation date: february 2017

Phase I clinical study to evaluate the safety and tolerability of PRO-165 ophthalmic gel versus Artelac® Nightime Gel on the ocular surface of ophthalmologically and clinically healthy subjects

Protocol code:SOPH165-0217/I

Protocol version:4.0

Version date: 21/Jan/2022

Clinical Trial ID: NCT04704531

Sponsor: Laboratorios Sophia, S.A. de C.V.

1. Summary

Title of the study:	
Estudio clínico fase I, para evaluar la seguridad y tolerabilidad del gel oftálmico PRO-165 versus Artelac® Nightime Gel, en la superficie ocular de sujetos oftalmológicamente y clínicamente sanos.	
Protocol code: SOPH165-0217/I	Creation date: February 7, 2017
Protocol version: 4.0	Version date: January 21, 2022
Therapeutic indication: Eye lubricant	
Study period: 4 months	Development phase: I
Aim: To evaluate the safety and tolerability of the PRO-165 formulation on the ocular surface of ophthalmologically and clinically healthy subjects.	
Hypothesis: PRO-165 ophthalmic gel presents a safety and tolerability profile similar to Artelac® Nightime Gel in ophthalmologically and clinically healthy subjects.	
Methodology: Phase I, controlled, parallel-group, double-blind, randomized, exploratory clinical study.	
Number of patients: 32 subjects, divided into 2 groups [16 subjects (16 eyes) exposed per group]	
Diagnosis and main inclusion criteria: 
 - Systemically and ophthalmologically healthy subjects - Signed informed consent. - Age between 18 and 45 years. - Both sexes - Blood tests [complete blood count (CBC), three-element blood chemistry (BC), and liver function tests (LFTs)] within normal parameters - Visual capacity 20/30 or better 	
Test product, dose and route of administration, 
 - PRO-165 Sodium hyaluronate 0.2% ophthalmic gel. Manufactured by Laboratorios Sophia , SA de CV, Zapopan, Jalisco, Mexico. 
 ▪ Dosage: One drop of gel, 4 times a day during the waking period, in the fornix of the right eye. 	

▪ Route of administration: ophthalmic
Treatment duration: 10 days
Reference product, dosage and route of administration:
1. Artelac ® Nighttime Gel. Carbomer 0.2%, ophthalmic gel. Made in Germany by: [name] Chem Pharm. Fabrik GmbH [name] . Imported and marketed by: Bausch & Lomb México, SA de CV, [name]
Evaluation criteria:
Primary safety outcome variables:
- Presence of adverse events.
Secondary outcome variables:
- Tear film break-up time - Vital signs: HR, RR, SBP. - Posterior segment - Intraocular pressure. - Visual capacity. - Laboratory tests: BHc , QS and PFH. - Ocular surface stains.
Primary tolerability outcome variables:
- Eye comfort index
Statistical methodology:
Data will be expressed using measures of central tendency. Qualitative variables will be presented as frequencies, proportions, and/or percentages. Statistical analysis will be performed using the Kruskal-Wallis test for quantitative variables. Differences between qualitative variables will be analyzed using the χ^2 test or Fisher's exact test. An alpha ≤ 0.05 will be considered significant.

2. Content

1. SUMMARY	1
2. CONTENT	3
3. INDEX OF ABBREVIATIONS	7
4. ADMINISTRATIVE STRUCTURE OF THE STUDY	9
5. INTRODUCTION	11
5.1 THEORETICAL FRAMEWORK	11
5.2 BACKGROUND	15
5.2.1 SODIUM HYALURONATE	15
5.2.1.1 Pharmacokinetics in the eyeball	16
5.3 PROBLEM STATEMENT	16
5.4 JUSTIFICATION	16
5.5 OBJECTIVES AND HYPOTHESES	17
5.5.1 GENERAL OBJECTIVE	17
5.5.2 SPECIFIC OBJECTIVES	17
5.5.3 SECONDARY OBJECTIVES	17
5.5.4 HYPOTHESIS	17
5.6 STUDY DESIGN AND PLAN	17
5.6.1 DISCUSSION OF THE STUDY DESIGN	17
6. MATERIALS AND METHODS. PARTICIPANTS, INTERVENTIONS AND VARIABLES	18
6.1 STUDY CENTER	18
6.1.1 ORGANIZATION OF THE CENTER	18
6.1.2 DOCUMENTATION TO BE DELIVERED TO THE SPONSOR	18
6.1.3 CLOSURE OF THE CENTER	19
6.2 ELIGIBILITY CRITERIA	19
6.2.1 INCLUSION CRITERIA	19
6.2.2 EXCLUSION CRITERIA	19
6.2.2.1 General criteria	19
6.2.2.2 Medical and therapeutic criteria	19
6.2.3 ELIMINATION CRITERIA	20
6.2.4 SUBJECT IDENTIFICATION	20
6.3 INTERVENTION	20
6.3.1 TREATMENTS ADMINISTERED	20
6.3.1.1 Treatment under study	20
6.3.1.2 Reference treatment	21

6.3.2 STRATEGIES TO IMPROVE ADHERENCE AND PROCEDURE TO MONITOR ADHERENCE	21
6.3.2.1 Procedure for monitoring adherence	22
6.3.3 CONCOMITANT TREATMENTS AND INTERVENTIONS PERMITTED AND PROHIBITED DURING THE STUDY	23
6.3.4 TREATMENT MANAGEMENT	23
6.3.4.1 Delivery and reception	23
6.3.4.2 Storage	24
6.3.4.3 Return	24

5.1 Theoretical framework

Dry eye disease (DED) Eye Eye disease is a common ocular condition that significantly diminishes quality of life and affects 6–34% of the adult population worldwide. [1] [2] Although there are no formal studies on the prevalence of the disease in Latin American countries, several reports suggest a higher prevalence of severe symptoms and clinical diagnosis of DED in the Hispanic population compared to the Caucasian population.[2] [3]

DED is a tear film disorder that results in damage to the ocular surface and is associated with symptoms of ocular discomfort. DED has also been called *keratoconjunctivitis. sicca* (KCS), sicca syndrome , xerophthalmia, dry eye syndrome, ocular surface disease, tear film dysfunction syndrome (TPDS), or simply dry eye. Strictly speaking, some of these terms are not synonymous, since, for example, DED can occur without keratitis, KCS; this protocol will use TPDS as [4] [5] a synonym for DED, assuming that they are interchangeable concepts and adopting the definition of the 2007 International Dry Eye Workshop (DEWS). Eye Workshop :

Dry eye is a multifactorial disorder of the tear film and ocular surface that causes symptoms of discomfort, visual disturbances, and tear film instability with potential damage to the ocular surface. It is accompanied by increased tear film osmolarity and inflammation of the ocular surface. [4]

LPDS is an alteration of the lacrimal functional unit (LFU), an integral system comprising the lacrimal glands, ocular surface (cornea, conjunctiva and meibomian glands), eyelids and the afferent and efferent nervous network that interconnects them. [6]

This LFU controls the main components of the tear film and regulates them in response to environmental, endocrinological, and cortical influences. Its main function is to preserve the integrity of the tear film, the transparency of the cornea, and the quality of the image projected onto the retina. [6] [7] [8] [9]

Damage or disruption to any component of the UFL can destabilize the tear film and lead to ocular surface disease manifested as PLDS. Tear film stability, a hallmark of a normal eye, is threatened when interactions between tear film-stabilizing components are compromised by decreased secretion, delayed clearance, and altered tear composition. Inflammation is a secondary consequence. Reflex tear secretion, in response to irritation, is considered the initial compensatory mechanism, but over time, inflammation accompanying secretory dysfunction and decreased corneal sensitivity compromises the reflex response and results in further tear film instability. Disruption of the UFL is considered to play a critical role in the development of various forms of dry eye. [4]

The tear film is a highly specialized and carefully structured moisturizing layer that covers the cornea and conjunctiva. It has been classically described as a trilaminar structure composed of a lipid surface layer, an aqueous intermediate layer, and an internal mucinous layer . [10]Currently, it is considered a hydrated gel with a concentration gradient of its components, mucin, water/electrolytes, proteins, and other components such as immunoglobulins. [7]The tear film has four main functions: 1) Maintain a regular optical surface, 2) Prevent friction between the structures of the ocular surface, 3) Nourish the cornea, and 4) First line of defense against ocular surface infections.[11]

Based on models of the tear film's "microstructure" and its interface with ocular surface cells, the mucin layer should always be present in a healthy tear film. [10] This layer provides support for the rest of the tear film on the ocular surface, helping to keep it moist and lubricated. [12] The epithelial cell layer of the conjunctiva includes goblet cells, which secrete mucin. These cells are the main source of mucin for the tear film. [11]

Within the framework of the DEWS, the etiopathogenic classification of PLDS was established, which is summarized in **Figure 1**. This classification aims to provide a more up-to-date understanding of PLDS. It is divided into two main classes: aqueous deficiency and evaporative. The aqueous deficiency category primarily refers to a failure of tear secretion. The evaporative class has been subdivided to distinguish between causes that depend on intrinsic conditions of the eyelids and ocular surface and those that arise from extrinsic influences.

PLDS can begin in either class, but these are not mutually exclusive. It is recognized that a disease can begin in one major class and coexist or even lead to events that produce PLDS through a mechanism in another class. This is part of a vicious cycle of interactions that can amplify severity. An example of this is that all forms of PLDS cause goblet cell loss, which over time will contribute to a loss of tear film stability, surface damage, and evaporative water loss. [4]

Many pathophysiological mechanisms of PLPS stimulate the sensory nerves of the cornea, which is why PLPS is described as a "symptomatic disease." [13] [14] [15] In most patients, there is a relationship between symptoms and clinical signs; however, it is also recognized that in some patients, the severity of symptoms does not correspond to the clinical signs of the disease. [14] [16] [17]

Classifying PLPS according to severity is currently challenging, as there is no gold standard for determining its severity; however, disease severity is one of the most relevant factors when considering therapeutic options for PLPS. [18] In 2006, a panel of specialists called the Delphi Panel issued a severity classification, later adopted by the DEWS. Severity was classified into four levels, based on the increasing frequency and intensity of various signs and symptoms. [18] See **Table 2**

There are other systems for classifying the severity of PLDS referred to by other authors, [19] [20] [21] [22] including the *European Consensus algorithm of the ODISSEY group*, which classifies discordant PLDS cases as severe, which are therefore more difficult to classify. [23]

In addition to the most highly correlated diagnostic methods for PLDS (OSDI, TRL, Schirmer test), conjunctival impression cytology (CIC) has recently been used. CIC is a minimally invasive technique that evaluates the characteristics of goblet cells. This technique can be used for diagnostic purposes, to elucidate the mechanism of the disease, and to evaluate treatment efficacy. [24]

[figure not shown]
Figure 1Classification of SDPL by etiology

Table 2Classification of SDPL by severity

Degree	1 Light	2 Moderate	3 Severe	4* Disabling
Discomfort, severity and frequency	Mild and/or episodic; occurs under environmental stress	Moderate episodic or chronic, with or without stress	Frequent or constant severe without stress	Severe and/or disabling and constant
Visual symptoms	None or mild episodic fatigue	Annoying and/or limiting episodic	Chronic and/or constant limiting discomfort	Constant and/or possibly disabling
Conjunctival injection	None to mild	None to mild	+	+/++
Conjunctival staining	None to mild	Variable	Moderate to marked	Marked
Corneal staining	None to mild	Variable	Marked center	Severe and widespread punctate erosion
Tear/corneal signs	None	Light debris, decreased meniscus	Filamentous keratitis, mucus aggregation, increased debris in tears	Filamentous keratitis, mucus aggregation, increased debris in tears, ulcer
Meibomian glands / eyelids	Meibomitis present variably	Meibomitis present variably	Frequent	Trichiasis, keratinization, symblepharon
TRL	Variable	≤ 10	≤ 5	Immediate
Schirmer I	Variable	≤ 10	≤ 5	≤ 2

*Must have signs and symptoms.

Adapted from Behrens A, Doyle JJ, Stern L, et al.[18]

The treatment currently available for SDPL can be divided into:

- Tear supplements: lubricants.
- Tear retention: tear punctum occlusion, contact lenses.
- Stimulation of secretion: secretagogues .
- Biological substitutes: autologous serum, salivary gland autotransplant.
- Anti-inflammatory drugs: cyclosporine, steroids, tetracyclines.
- Essential fatty acids
- Environmental strategies

Recommended practices in dry eye by the American Academy of Ophthalmology and the Delphi Panel of the International Task Force Force , ITF) on the treatment of dry eye, favored, in turn, by the DEWS, are based on the severity of the disease See **Table 3**. The recommendations may be modified by the ophthalmologist, based on clinical experience and the individual profile of his patient. [18] [25] [26]

Table 3Treatment recommendations for LPDS

Level 1:
Education and dietary and environmental modifications
Elimination of systemic medications that alter UFL
Lubricants
Eyelid treatment
Level 2:
If level 1 treatments are insufficient, add:
Anti-inflammatories
Tetracyclines
Tear plugs
Secretagogues
Level 3:
If level 2 treatments are insufficient, add:
Autologous serum
Contact lenses
Permanent occlusion of tear ducts
Level 4:
If level 3 treatments are insufficient, add:
Systemic anti-inflammatories
Surgery (tarsorrhaphy, transplantation: mucous membrane, salivary gland, amniotic membrane)

Modified from the ITF [18]

The primary goal of caring for patients with PLDS is to improve ocular comfort and quality of life, as well as to return the ocular surface and tear film to a state of homeostasis. Although symptoms are rarely eliminated, they can often be reduced, resulting in improved quality of life. [26]

Ocular lubricants are the first line of treatment for PLDS and a constant at all treatment levels. They are characterized as hypotonic or isotonic solutions containing electrolytes, surfactants, and various types of viscosifying agents. The main variables in ocular lubricant formulations relate to the selection or concentration of electrolytes, osmolarity, the type of viscopolymer system, and the presence or absence of preservatives. [26]

5.2 Background

5.2.1 Sodium hyaluronate

It is a biopolymer, a disaccharide of the GAG family, formed by the alternating sequence of N-acetyl-D-glucosamine and glucuronate in linear chains. In physiological solvents, they form spirals; their configuration is determined by their viscosity. It is a constituent of the extracellular matrix, connective tissue, vitreous humor, umbilical cord, synovial fluid, skin, etc. It can be composed of more than 10,000 disaccharide pairs. At concentrations above 0.1%, sodium hyaluronate forms a network. The diffusion rate through the network is inversely related to the size of the polysaccharide molecules, which are stable. Proteoglycans contribute to providing mechanical and elastic properties. Numerous authors have reported that HS has a high water-retaining capacity; it has been established that 1 g of HS can retain up to 6 L of water. [28]

Sodium hyaluronate is synthesized on the inner surface of the plasma membrane as a linear polymer, in contrast to other GAGs, which are synthesized by enzymes in the Golgi apparatus. The

enzymes responsible for the synthesis of sodium hyaluronate are hyaluronate and glucosyltransferases , which coordinately polymerize and translocate sodium hyaluronate outside the cell into the extracellular matrix. [29]

5.2.1.1 Pharmacokinetics in the eyeball

Route of administration: Ophthalmic.

Release: immediate.

Absorption: No absorption of HS through the cornea has been reported when applied to the ocular surface. Pharmacokinetic studies conducted in patients with dry eye showed that the HS solution reached its maximum concentration within 10 minutes and is widely distributed across the ocular surface.

Metabolism: It is biotransformed by hyaluronidases.

Elimination: It is eliminated from this compartment through the lacrimal sac and tear duct without intraocular absorption, in approximately 45 minutes. [30]Based on the results of preclinical research in rabbits conducted by Laboratorios Sophia SA de CV, the ocular half-life correlates with the volume of the formula.

5.3 Problem Statement

There are few effective treatments for PLDS. Clinical development of new treatments is slow due to the multiple pathogenesis of PLDS and its variable semiotics. The different treatment phases have a common denominator: the use of ocular lubricants.

Although there is a wide variety of topical lubricants, with different viscosifying agents, there is no evidence that one is better than another.

Although ocular lubricants have not been shown to be sufficient to completely resolve the ocular surface alteration and inflammation seen in patients with PLDS, they have been shown to provide protection to the ocular surface and reduce symptoms and clinical findings.

Sodium hyaluronate (SHN) is a biopolymer, glycosaminoglycan (GAG), a constituent of the extracellular matrix. It provides PRO-165 with viscoelastic and water-retaining properties, enabling it to function as an effective lubricant that protects the ocular surface and reconstructs the tear film. Formulating it as an ophthalmic gel can provide a longer dwell time, promoting prolonged lubrication. Currently, the range of lubricants in ophthalmic gels is not as extensive as that of solutions. Therefore, adding a new option to this group of pharmaceutical formulations will contribute to improved care for patients with PLDS.

5.4 Justification

Patients with LPDS, regardless of its etiology and severity, will need to use ocular lubricants to reduce symptoms and improve their quality of life.

Ocular lubricants are the first-line treatment for ocular symptoms related to tear film dysfunction in self-reported healthy subjects, with a prevalence of 5% to 35% in those over 50 years of age. [32]If we add to this the number of patients who report occasional symptoms or symptoms that are dependent on a work or occupational situation and who will use them intermittently throughout their lives, the population spectrum that will have access to these medications is very broad. It is

estimated that 50% of patients diagnosed with tear film dysfunction without concomitant diseases will use more than two types of ophthalmic solutions in 5 years of treatment.

PRO-165 is an ophthalmic gel lubricant formulation for which a safety profile must be documented.

5.5 Objectives and hypotheses

5.5.1 General Objective

To evaluate the safety and tolerability of the PRO-165 formulation on the ocular surface of ophthalmologically and clinically healthy subjects.

5.5.2 Specific objectives

- To describe the safety of PRO-165 ophthalmic gel by presenting adverse events.

5.5.3 Secondary Objectives

- To describe the safety of PRO-165 ophthalmic gel through changes in intraocular pressure.
- To describe the safety of PRO-165 ophthalmic gel through changes in visual ability.
- To describe the safety of PRO-165 ophthalmic gel through changes in laboratory testing.
- To describe the safety of PRO-165 ophthalmic gel when evaluating ocular surface stains
- To describe the safety of PRO-165 ophthalmic gel through changes in tear break-up time.
- To describe the safety of PRO-165 ophthalmic gel through changes in vital signs.
- To describe the tolerability of PRO-165 ophthalmic gel by the presence of the symptoms: burning, foreign body sensation, and itching.

5.5.4 Hypothesis

H_0 PRO-165 ophthalmic gel presents a safety and tolerability profile similar to Artelac® Nighttime Gel in ophthalmologically and clinically healthy subjects

H_1 PRO-165 ophthalmic gel presents a different safety and tolerability profile than Artelac® Nighttime Gel in ophthalmologically and clinically healthy subjects.

5.6 Study design and plan

Phase I, controlled, parallel-group, double-blind, randomized, exploratory clinical trial.

5.6.1 Discussion of the study design

The study design (clinical trial) is considered the highest standard of data quality when exploring the effect of an intervention. The drug development phase (Phase I) corresponds to the study objective, which is to evaluate safety and tolerability. Therefore, the intervention time is short and the required sample size is smaller than that of an efficacy clinical trial. The presence of parallel groups allows for comparisons between intervention groups on outcome variables. Blinding and randomization reduce biases that occur with other designs, e.g., selection bias, assessment bias, among others.

The selection of Artelac® Nighttime Gel was based on the need to compare PRO-165 with a treatment with the same formulation and the same indication as PRO-165. Although they do not share the same active ingredients, this does not limit their comparability, as no pharmacological action is expected from either treatment. Since there is no ophthalmic gel with the same concentration of the active ingredient as PRO-165, and since comparison with placebo is not feasible due to technical difficulties, Artelac® Nighttime Gel is an option for conducting a comparative Phase I study.

6. Materials and methods. Participants, interventions, and variables

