6.3 Intervention

6.3.1 Treatments administered

6.3.1.1 Treatment under study

- **PRO-165**
 - Active ingredients (lubricant): sodium hyaluronate 0.2%
 - Pharmaceutical form: Ophthalmic gel
 - Prepared by: Laboratorios Sophia , SA de CV
 - Dosage: One drop of gel, 4 times a day during the waking period, in the fornix of the right eye.

- Formulation description: Clear gel, free of visible particles.
- Packaging description: Sterile multi-dose tube, low-density polyethylene and aluminum polylaminate with high-density polyethylene cap.

Table 4Qualitative -quantitative formulation of PRO -165

Agent type	Amount mg/ mL	Function
Sodium hyaluronate	2.0	Active ingredient
Chondroitin sulfate	Not shown	Viscosant
Polyoxylated Castor Oil 35	Not shown	Solubilizer
Polyethylene glycol 8000¹	Not shown	Cosolvent
Eddate disodium dihydrate	Not shown	Chelating agent
Cetrimide	Not shown	Conservative
Glycerin	Not shown	Osmoregulator
Sodium hydroxide	Not shown	pH adjustment
Homopolymer carbomer type B²	Not shown	Gelling agent
Polycarbophil³	Not shown	Gelling agent
Water for the preparation of injectables cbp⁴	Not shown	Vehicle

Qualitative and quantitative formulation of the investigational product PRO-165. The concentration of the active ingredient is shown, as well as the substances that act as additives. (1) Synonym of Carbowax® (2) Synonym of Carbopol® 974P NF Polymer, USP (3) Synonym of Noveon® AA-1 Polycarbofil, USP (4) as much as is sufficient for

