6.3.1.2 Reference treatment

- **Artelac® Nightime Gel**
- Active ingredients: Carbomer 0.2%
- Pharmaceutical form: Ophthalmic gel
- Prepared by: [name] Chem Pharm. Fabrik GmbH [name] . Imported and marketed by: Bausch & Lomb México, SA de CV, [name].
- Dosage : One drop of gel, 4 times a day during the waking period, in the fornix of the right eye.
- Solution description: Clear gel, free of visible particles.
- Packaging description: Sterile multi-dose tube.
- Characterization: The characterization, stability, and formulation of the comparator will be supported by its packaging, lot number, and IPP, a copy of which will be kept in the study's master folder.

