6.6.1 Sample size calculation

There are no references on the calculation of the sample size in phase I studies, and the formulation of Humylub Ofteno® has not reported any adverse events in its periodic safety reports. Therefore, it was considered appropriate to base the calculations on previous phase I studies conducted by Laboratories . Sophia , SA de CV [45, 46, 47, 48].

The calculation was based on the adverse event presentation reported by Christ T., in a randomized, single-blind, parallel-group controlled clinical trial evaluating the efficacy and tolerability of a 5% dexamphenol ophthalmic gel versus a 5% panthenol ointment in 48 subjects with corneal erosion, UV-induced keratoconjunctivitis, or similar conditions. The intervention consisted of applying 1 cm of the gel and ointment for 4 and 3 days, respectively.[49]

The percentage of good tolerance reported with the gel was 25%, so it is expected that no more than 10% of subjects will report poor tolerance with the formulation proposed in this protocol.

The sample size was calculated using the formula for proportions

$$n = p (1 - p) \left(\frac{Z_{1-\alpha} + Z_{1-\beta}}{p - p_0 - \delta} \right)^2$$

With a statistical confidence of 95% corresponding to type I error, equal to 1.96, with a power of 90%, corresponding to type II error, equal to 0.84.

According to the previous calculation, the result is 26 subjects, which was increased by 20% to account for probable losses. The total required sample size is **32 subjects** . Therefore, each group will consist of 16 subjects, each of whom will contribute an eye to the analysis.

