For adverse event reporting, all eyes of participants randomized to an intervention group after the baseline visit will be considered. Results will be expressed as the number of cases (eyes).

The final results report will be displayed in tables or graphs, as appropriate.

The investigational drug will be considered safe and tolerable when there are no clinical or statistical differences in all primary outcome variables compared to its comparators.

Subjects with an adherence rate greater than 60% will be included in the statistical analysis to meet the study objective, based on the subject's diary. However, even if the subject's diary indicates adherence greater than 60%, if the adherence calculated by weight is less than 30%, the subject will not be included. The minimum dose necessary to obtain a pharmacological effect (lubricant/1 gel application per day) and the presence of adverse events (exposure) were considered sufficient to meet the overall design objective, in accordance with the pharmacological characteristics of the investigational product.

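### The rule for calling PRO-165 safe and tolerable is wholly relative to the comparator, so non-serious harm common to both gels would very probably pass it

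*Protocol*

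**What the plan says.** **The rule.** Protocol 8.3.1 says the product will be "considered safe and tolerable when there are no clinical or statistical differences in all primary outcome variables compared to its comparators". The SAP (Methods of Analysis, just before Table 3) repeats the rule and names Artelac Nighttime Gel as the comparator. The primary variables are adverse events and the Eye Comfort Index (ICO).

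**The objectives.** Protocol 5.5.1 asks about the safety and tolerability of PRO-165 itself, and 5.5.2 sets the aim "To describe the safety of PRO-165 ophthalmic gel by presenting adverse events". The hypothesis in 5.5.4 is comparative: a profile similar to Artelac.

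**The comparator.** Section 5.6.1 states: "Although they do not share the same active ingredients, this does not limit their comparability, as no pharmacological action is expected from either treatment". It adds that "comparison with placebo is not feasible due to technical difficulties". Table 4 (6.3.1.1) lists "Homopolymer carbomer type B" as a gelling agent in PRO-165, with the amount not shown. Section 6.3.1.2 gives the reference product as "Active ingredients: Carbomer 0.2"%. Section 5.6.1 does not mention that carbomer is in both.

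**Absolute figures elsewhere.** Two exist, and neither is part of the rule. Section 6.6.1 says "it is expected that no more than 10% of subjects will report poor tolerance with the formulation proposed in this protocol", which is used only for sample size. Section 9.2 makes serious adverse events in more than 5% of either arm a ground for considering early termination.

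**The concern.** A between-arm comparison cannot see an effect that occurs equally in both arms. That is acceptable when the conclusion is also comparative. Here the conclusion is absolute (safe and tolerable) while the evidence required for it is only the absence of a difference from another gel. There is no placebo or vehicle arm, and neither document gives a tolerability rate for Artelac in healthy eyes at this regimen that would turn likeness to Artelac into an absolute statement.

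At stake is what the trial may say about PRO-165. If both gels produced frequent mild irritation, a report that followed the plan to the letter could still call PRO-165 safe and tolerable. This is a separate matter from low power: the problem remains when the two true rates are exactly equal, whatever the sample size.

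**Working it through.** **Inputs**
- 16 subjects per arm, 1:1 (Protocol 6.6 and 7.1). The last step of the sample-size section reproduces: 26 × 1.2 = 31.2, rounded up to 32, and 32/2 = 16. How the 26 arises does not matter here.
- Adverse events are compared by Pearson chi-square, or by Fisher's exact test when expected values are below 5 (SAP, Methods of Analysis).
- Significance at 0.05. Sidedness is not stated; I assume two-sided.
- ICO is compared by a rank test at the same level (SAP Table 2).

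**Step 1. Observed equality passes at any level.**
- 8/16 against 8/16: expected counts are 8, so chi-square applies; the statistic is 0 and p = 1.0 (Fisher also gives 1.0). The exact (Clopper-Pearson) 95% CI for the PRO-165 rate is 24.7% to 75.3%.
- 4/16 against 4/16: expected counts of 4 call for Fisher; p = 1.0. The exact 95% CI for the PRO-165 rate is 7.3% to 52.4%.

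The statistical limb is met for adverse events in both cases.

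**Step 2. Probability of passing when true rates are equal.** Let X and Y be independent Binomial(16, π). Sum P(X = i)·P(Y = j) over all tables where the SAP's test gives p > 0.05. For the ICO test, multiply by 1 − 0.05 = 0.95, which assumes nominal size, no true ICO difference and independence of the two tests.

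| Common true rate π | No significant AE difference | × 0.95 for ICO |
|---|---|---|
| 10% | 99.3% | 94.4% |
| 25% | 97.3% | 92.4% |
| 50% | 95.0% | 90.2% |
| 75% | 97.3% | 92.4% |
| 90% | 99.3% | 94.4% |

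The pass probability barely responds to the absolute level of harm. With 13 per arm (26/2, if all the allowed losses occur) the 50% row becomes 93.4% and 88.7%.

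**Step 3. Effect of a larger sample.** Under equal rates, a test of size 0.05 is non-significant about 95% of the time at any n, so both tests pass about 0.95 × 0.95 = 90% of the time. Adding subjects does not help.

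**Step 4. What a pass does show.** The approximate 95% CI for the difference is 0 ± 1.96·√(2π(1−π)/16).
- At 8/16 in each arm: 1.96·√(2 × 0.25/16) = 1.96 × 0.177 = ±35 percentage points.
- At 4/16 in each arm: 1.96·√(2 × 0.1875/16) = 1.96 × 0.153 = ±30 points.

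Even as a comparative statement, a pass supports no difference detected. It does not establish similarity.

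**Step 5. What the PRO-165 arm alone can show.** Exact 95% CIs: 0/16 gives 0% to 20.6%; 1/16 gives 0.2% to 30.2%; 2/16 gives 1.6% to 38.4%.

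**The case against.** The strongest reply is that much of this is already covered.

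- The hypothesis claims only similarity, and the trial is labelled exploratory.
- SAP Table 2 defines adverse-event frequency as subjects with events over subjects exposed, with intensity and causality, so the PRO-165 rate will be visible.
- Within-group Wilcoxon and McNemar tests could reveal change from baseline that the between-arm test hides.
- One serious event in 16 (6.25%) already exceeds the 5% figure in 9.2.

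All of this stands, and it limits the point to non-serious harm and to the wording of the conclusion. It does not remove the point: none of these results feeds the rule, and the rule states more than the hypothesis does. The SAP's mention of a 95% CI for non-inferiority does not help either, since no margin is given and non-inferiority would still be relative to Artelac.

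Several stronger readings are tempting but unsupported:

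- **That 5.6.1 is false.** Its sentence on active ingredients is literally correct, because carbomer is an excipient in PRO-165. The gap is that comparability is argued from active ingredients alone.
- **That carbomer irritates and its effect cancels between arms.** The documents show no harm from carbomer. Its amount in PRO-165 is withheld, so equal exposure cannot be shown.
- **That the whole base is shared.** Polycarbophil and cetrimide are in PRO-165, but nothing shows them in the comparator. If they are only in PRO-165, the comparison can detect their effects.
- **That a 50% event rate breaches the 10% expectation in 6.6.1.** That expectation concerns poor tolerance, which is undefined. Adverse events are counted without regard to cause, so the two are different endpoints. The 25% and 50% rates above are illustrations, not forecasts.

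**Conclusion.** The concern holds as a gap between rule and conclusion. Because both limbs refer to the comparator, the plan can declare PRO-165 safe and tolerable without any absolute result for PRO-165 having been weighed. With 16 per arm and equal true rates, the adverse-event test passes in 97.3% of trials at a 25% rate and 95.0% at 50%. About 90% or more pass both primary tests.

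These figures assume two-sided tests at 0.05, all 16 subjects per arm analysed, no true ICO difference, and independence of the two tests. They cover the statistical limb only. The clinical limb has no stated criterion, though it too is worded as a difference from the comparator. A reader might infer that shared harm is certain to be declared safe; the documents support very probably, and only for non-serious harm. The gap exists for any cause common to both gels, with carbomer as one concrete possibility.

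**What to change.** 1. In Protocol 8.3.1 and the SAP's Methods of Analysis, limit the between-arm conclusion to a statement that no difference from Artelac Nighttime Gel was detected, reported with the 95% CI for the difference.
2. Base any statement that PRO-165 itself is safe and tolerable on the PRO-165 arm. Report the proportion of subjects with a treated-eye adverse event and its exact 95% CI, and the ICO change from baseline with a 95% CI. Count subjects and the right (dosed) eye; 8.3.1 at present reports cases over all eyes.
3. Add to 5.6.1 that both gels contain carbomer, and that effects common to both cannot be seen in the comparison.

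A poor-tolerance proportion should not be added as things stand. Neither document defines poor tolerance, and the ICO is a 0–100 score with no cut-off. Its questions ask about the eyes in general, so even the ICO change will not isolate the treated eye; the report should say so.

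The cost is wording in two documents and a few intervals from data already planned, with no new subjects or visits. The price is a narrower headline claim and wide intervals: even 0/16 leaves an upper limit of 20.6%.
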